Lactoferrin Infant Feeding Trial: LIFT Statistical Analysis Plan

Prepared by:	[name] NHMRC Clinical Trials Centre	
	University of Sydney	
Version:	1.0	
Version date:	15MAR18	
Approved by:	[name]	(Name)
	SENIOR BIOSTATISI	4besignation)
	[name]	(Signature)
	19-3-18	(Date)
11/14	[name]	(Name)
PRIM	ICPKI INVESTIGATION	(Designation)
M	[name]	(Signature)
	19/3/2018	(Date)

Contents

1	Intr	oduction	3
2	End	points	3
	2.1	Morbidity-Free Survival to Hospital Discharge (Primary Endpoint)	4
	2.2	Survival to Hospital Discharge	4
	2.3	Brain Injury at 36 Weeks Corrected Gestational Age	4
	2.4	Necrotising Enterocolitis of Grade II or Higher at 36 Weeks Corrected Gestational Age	5
	2.5	Late Onset Sepsis at 36 Weeks Corrected Gestational Age	5
	2.6	Treatment for Retinopathy (to Discharge)	5
	2.7	Time to Full Enteral Feeds	5
	2.8	Number of Blood Transfusions to 36 Weeks Corrected Gestational Age	5
	2.9	Chronic Lung Disease at 36 Weeks Corrected Gestational Age	6
	2.10	Length of Hospital Stay	6
	2.11	Survival and Development Outcomes at 24 to 36 Months Corrected Gestational Age	6
	2.12	Safety	7
3	Ana	lysis Sets	7
4	Inte	rim and Final Analyses	7
5	Тур	e I Error (Alpha)	7
6	Ana	lysis of Study Endpoints and Patient Characteristics	7
	6.1	Subject Disposition	8
	6.2	Baseline Demographic and Clinical Characteristics	8
	6.3	Duration of Study Treatment	8
	6.4	Morbidity-Free Survival to Hospital Discharge (Primary Endpoint)	8
	6.5	Analysis of Categorical Secondary Endpoints	8
	6.6	Analysis of Quantitative Secondary Endpoints	9
	6.7	Safety Data Analysis	9
7	Sub	group Analyses	9
8	Adju	usted Analyses	10
	8.1	Stratification Factors	10
	8.2	Treatment Compliance	10
9	Synt	thesis of Trial Evidence	
	9.1	Cochrane review	11
	9.2	LIFT_Canada	11
11) Rofe	arences.	12

1 Introduction

The aim of LIFT (Lactoferrin Infant Feeding Trial) is to determine the effectiveness of adding bovine lactoferrin (bLF) to the feeds of preterm babies of less than 1500 g birth weight. The key eligibility criteria are: <1500 g birth weight, ≤7 days old and expected to survive, and no severe congenital anomalies that are likely to cause death.

LIFT is a multicentre phase III trial that randomises eligible babies to the experimental group receiving bLF added to breast milk or formula milk once daily, or to the control group receiving no bLF added to breast milk or formula milk. These strategies (hereafter referred to as treatments) are intended to continue until 34 weeks corrected gestation or for 2 weeks, whichever is longer, or until discharge home, if earlier.

The randomisation is performed using a centralised system that allocates patients in a 1:1 ratio via minimisation stratified by site, gender, birth weight ($<1000 \text{ vs} \ge 1000\text{-}1499\text{g}$), and according to whether the baby is from a single or multiple birth.

LIFT is masked (i.e. treatment allocation is concealed from investigators, clinicians, parents, study personnel) however a designated person (e.g. bedside nurse, pharmacist, member of milk kitchen staff, or any appropriate staff member) prepares the milk feed containing either bLF (treatment group) or nothing (control group).

- This analysis plan provides additional detail to the LIFT protocol (Version 2.0, 20JAN17, ACTRN12611000247976) on endpoint derivations and planned analyses. The health economic
- analyses described in the protocol are not detailed in this analysis plan.

2 Endpoints

analysis plan).

The primary endpoint for the study is morbidity-free survival to hospital discharge. The key secondary short-term endpoints comprise the 5 components of the primary composite endpoint.

The other secondary short-term endpoints are: time to reach full enteral feeds; number of blood transfusions; chronic lung disease; length of hospital stay; and, financial costs (out-of-scope for this

The following section provides detailed instruction on the derivation of endpoints. Any instances where the application of these instructions is unclear for a given baby will be resolved via blinded clinical review and documented.

2.1 Morbidity-Free Survival to Hospital Discharge (Primary Endpoint)

- 2 The primary endpoint is a composite of survival to hospital discharge (Section 2.2) free from:
 - (1) major morbidity at 36 weeks corrected gestational age defined as:
 - brain injury (Section 2.3) or,
 - necrotising enterocolitis of Grade II or higher (Section 2.4) or,
 - late onset sepsis (Section 2.5); AND
- 7 (2) retinopathy treated according to local guidelines by discharge from hospital (Section 2.6).

8

1

3

4

5 6

- Babies that survive to discharge but have missing data for any of the morbidities listed above will be
- assigned a missing value for the primary endpoint. Babies with no missing data for any of the
- 11 morbidities AND who do not meet any of the morbidity criteria AND who survive to hospital
- discharge will be classified as having no event (i.e. event='No'). Babies that die prior to discharge
- and/or meet at least one of the morbidity criteria will be categorised as having had an event (i.e.
- event='Yes'). The estimated treatment effect will consequently reflect the impact of bLF on the
- 15 likelihood of death and/or morbidity.

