2.3 Brain Injury at 36 Weeks Corrected Gestational Age

- The endpoint 'Brain injury at 36 Weeks Corrected Gestational Age' will be derived using items from
- the "36 Weeks (OUTCOMES)" eCRF.

23

26

28

29

30

16

19

20

- 24 'Brain injury' will be set to 'Yes' if any of the following conditions are met:
- Worst grade of IVH seen (<14 day scan) [itmIVHGRADE] = "Grade 3" or 'Grade 4"
 - Echodense intraparenchymal lesions (>14 day scan) [itmlMECHO] = 'Yes'
- Periventricular leukomalacia (>14 day scan) [itmIMPERI] = 'Yes'
 - Porencephalic cysts (>14 day scan) [itmIMPOREN] = 'Yes'
 - Ventriculomegaly (97 percentile plus 4mm) (>14 day scan) [itmIMVENTRI] = 'Yes'
 - Hydrocephalus (>14 day scan) [itmlMHYDRO] = 'Yes'
- Encephaloclastic porencephaly (>14 day scan) [itmlMENCEPH] = 'Yes'

32 33

34

35

36 37

- 'Brain injury' will be set to 'missing' if:
 - the '<14 day scan' is performed >1 day late AND there is no grade 3-4 IVH identified; OR,
 - the '>14 day scan' is performed >1 day early AND none of the criteria applicable to this scan listed above are met; OR,
 - the '>14 day scan' is performed > 7 days after Week 36 AND deemed invalid on blinded clinical review.

38 39 40

'Brain injury' will be set to 'No' if none of the conditions above apply.

- Other types of brain injury recorded as free text in the database will undergo a blinded clinical
- 43 review against the criteria above.

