6.4 Morbidity-Free Survival to Hospital Discharge (Primary Endpoint)

- 13 The primary analysis will be a comparison between treatment groups on the proportion of babies
- 14 experiencing the primary composite endpoint that is tested using a Wald test (with a χ_1^2 distribution)
- 15 from a log-binomial model fitted using generalised estimating equations to accommodate possible
- 16 correlation of data between siblings from multiple births. If the log-binomial model does not
- 17 converge, a logistic model will be used.

18 19

8

12

- A multiple imputation approach will be used to account for missing primary endpoint data in a
- 20 sensitivity analysis. The effect of assuming all missing values are uniformly indicative of an 'event'
- 21 (pessimistic scenario) or of 'no event' (optimistic scenario) may also be explored.

22

25

- 23 Estimates of the treatment effect on the primary endpoint that are adjusted for stratification factors
- and adherence to assigned treatment will be produced using the methods detailed in Section 8.

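### Section 2.1 gives a survivor with one confirmed and one missing morbidity two primary endpoint values, 'missing' and 'Yes', and states no precedence

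*SAP*

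**What the plan says.** SAP Section 2.1 derives the composite in three sentences.

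- **Missing rule.** It covers "Babies that survive to discharge but have missing data for any of the morbidities listed above will be" given a missing primary endpoint. It makes no exception for a baby in whom another morbidity is already confirmed.
- **No-event rule.** A baby with every morbidity known, none met, and alive at discharge is 'No'.
- **Event rule.** Babies who die before discharge "and/or meet at least one of the morbidity criteria will be categorised as having had an event". It does not require the other components to be known.

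Three other places bear on this.

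- The introduction to Section 2 has a general fallback: "Any instances where the application of these instructions is unclear for a given baby will be resolved via blinded clinical review and documented".
- Section 2.3 can set brain injury to missing on scan timing, for example when "the '<14 day scan' is performed >1 day late AND there is no grade 3-4 IVH identified; OR", whatever the status of enterocolitis, sepsis or retinopathy.
- Section 6.4 uses multiple imputation for missing primary values in a sensitivity analysis only. It adds that coding all missing values as events ("pessimistic scenario) or of 'no event' (optimistic scenario) may also be explored") is a further option.

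**The concern.** A composite of death or any listed morbidity is settled once one component is positive. A survivor with proven late onset sepsis and no valid head scan is therefore a known event, yet the missing rule removes that baby from the primary analysis while the event rule keeps it.

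If the missing rule governs:

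- recorded events drop out, while deaths with missing morbidities stay in;
- the same baby counts as an event in the sepsis analysis of Section 6.5 but is absent from the composite that contains sepsis;
- imputation done at the level of the composite could turn the baby into a non-event, and the optimistic scenario would do so by rule.

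The same variable feeds the interim analysis (Section 4), the subgroup and adjusted analyses (Sections 7 and 8) and the planned pooling with the Canadian trial (Section 9.2).

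**Working it through.** **1. Do the rules overlap?** The SAP gives no figure to reproduce here, so the rules were applied literally to every pattern. Each of the four morbidities can be No, Yes or Missing, which gives 3^4 = 81 patterns for survivors and 81 for deaths.

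- Deaths: all 81 are 'Yes' only.
- Survivors with at least one Yes and at least one Missing: 81 − 16 (none missing) − 16 (none Yes) + 1 (all No, subtracted twice) = **50**. All 50 satisfy both the missing and the event rule.
- Remaining survivors: 15 'Yes' only, 15 'missing' only, 1 'No'.

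No pattern is left without a value. With the event rule first, each of the 162 patterns has exactly one value: 81 + 65 'Yes', 15 'missing', 1 'No'.

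**2. How far do the two readings differ?** The SAP passages at issue give no event or missing-data rate, so these inputs are assumptions: mortality d = 0.05; survivors s = 0.95; morbidity in survivors q = 0.18; e = s × q = 0.171; a proportion m of survivors has a component missing at random.

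- True event rate: d + e = 0.05 + 0.171 = 22.1%.
- Missing-first: (d + e(1 − m)) / (d + s(1 − m)).
- Event-first: (d + e) / (d + e + s(1 − q)(1 − m)).
- Known events lost under missing-first: N × e × m. With N = 1,500 assumed, all events number 1,500 × 0.221 = 331.5.

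| m | Missing-first | Event-first | Events lost |
|---|---|---|---|
| 5% | 0.21245/0.9525 = 22.3% | 0.221/0.96105 = 23.0% | about 13 |
| 10% | 0.2039/0.905 = 22.5% | 0.221/0.9221 = 24.0% | about 26 |
| 15% | 0.19535/0.8575 = 22.8% | 0.221/0.88315 = 25.0% | about 38 |

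This treats every affected survivor with a missing component as still having a recorded morbidity, so it overstates the loss where the missing component was the only positive one.

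**3. A version by component.** Let only brain injury go missing, at random, in 1% to 10% of survivors. Take brain injury/enterocolitis/sepsis/retinopathy rates in survivors of 5/3/10/3% (low) to 8/5/20/6% (high), independent of one another, with 5% mortality. Known events lost per 1,000 babies are 1,000 × 0.95 × m × P(another morbidity present).

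- Low rates, m = 1%: 9.5 × (1 − 0.97 × 0.90 × 0.97) = 1.5.
- High rates, m = 10%: 95 × (1 − 0.95 × 0.80 × 0.94) = 27.

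At m = 10% the observed rates, missing-first versus event-first, are 24.0% versus 25.2% (true 23.6%) with low rates, and 37.9% versus 39.7% (true 37.6%) with high rates.

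**4. Effect on the treatment comparison.** Use the inputs of step 2, with 750 babies per arm, a 20% relative reduction in both death and morbidity, equal missingness in the arms and no sibling correlation (all assumed). The treated-arm true rate is 0.04 + 0.96 × 0.144 = 17.8%, so the true relative risk is 0.178/0.221 = 0.807.

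- m = 10%: relative risk 0.807 missing-first versus 0.810 event-first; expected z 1.98 versus 2.04, about 3% lower.
- m = 15%: expected z 1.94 versus 2.03, about 5% lower.

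**The case against.** The best defence has five parts.

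- **The event sentence is just as unqualified as the missing sentence.** The composite definition and the closing line of Section 2.1 favour keeping the event. Section 2.3 points the same way: its first two missing conditions apply only if that scan shows no qualifying lesion. A reader might infer that the SAP plans to discard known events. The text does not support that, because coming first in the paragraph is not precedence. Discarding is one of two available readings.
- **Blinded clinical review covers unclear cases.** This protects against resolution by arm. It is written for a given baby, however, and here two rules collide for a whole class of babies. A programmer who applies either sentence gets a definite answer, so nothing need trigger review.
- **The overlap may be rare.** A reader might infer from Section 2.3 that it will be common, but no missing-data rate is given and the scan conditions are narrow. The early scan must be more than 1 day late with no grade 3-4 haemorrhage. The later scan must be more than 1 day early with none of its criteria met, or more than 7 days after week 36 and judged invalid on blinded review. A different morbidity must also be confirmed in the same survivor. This part stands.
- **Event-first alone lies further from the true rate in a complete-case analysis.** It keeps events with a missing component and drops possible non-events. This stands, and it shapes the fix.
- **The imputation harm is conditional.** It needs the missing-first reading and imputation of the composite itself; Section 6.4 does not fix the level, and the optimistic scenario is optional. This also stands.

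**Conclusion.** The contradiction holds on the wording alone and needs no assumed figure. The SAP sets no precedence; the protocol was not available for this check. The primary denominator and event count therefore depend on which sentence the programmer follows.

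The practical size is unknown. Under the assumptions above, the two readings differ by 0.7 to 2.2 percentage points in the observed event rate (23.0 − 22.3 to 25.0 − 22.8), and missing-first costs a modest amount of power. Bias between the arms is a tempting inference, but nothing in the SAP shows it: with equal missingness the relative risk hardly moves. Nor do the rates show that missing-first is the more distorting reading. Against the true 22.1% it is the closer of the two under these assumptions; its fault is that it sets aside recorded events. The point is worth correcting because it concerns the primary endpoint and the remedy is cheap.

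**What to change.** Replace the three sentences in Section 2.1 with an ordered rule:

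1. Death before discharge, or any morbidity criterion met: 'Yes', whatever else is missing.
2. Alive at discharge, all morbidities known and none met: 'No'.
3. Alive at discharge, no criterion met and at least one morbidity missing: 'missing'.

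Because this order alone raises the complete-case event rate, pair it with multiple imputation of the missing components for the babies in group 3, deriving the composite after imputation. State in Section 6.4 that the pessimistic and optimistic scenarios apply to group 3 only. A recorded event then cannot be imputed or scenario-coded as a non-event.

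The cost is a few lines of SAP text and derivation code, with no new data, settled before the derivation is run on unblinded data. The one drawback is a somewhat higher complete-case event rate unless the group 3 babies are imputed.

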2.2 Survival to Hospital Discharge

- 17 Death is set to 'yes' if the following condition is met by data captured on the "Discharge
- 18 (DISCHARGE)" eCRF:
 - Was the baby alive at discharge? [itmSTATUS]='No'

2.3 Brain Injury at 36 Weeks Corrected Gestational Age

- The endpoint 'Brain injury at 36 Weeks Corrected Gestational Age' will be derived using items from
- the "36 Weeks (OUTCOMES)" eCRF.

23

26

28

29

30

16

19

20

- 24 'Brain injury' will be set to 'Yes' if any of the following conditions are met:
- Worst grade of IVH seen (<14 day scan) [itmIVHGRADE] = "Grade 3" or 'Grade 4"
 - Echodense intraparenchymal lesions (>14 day scan) [itmlMECHO] = 'Yes'
- Periventricular leukomalacia (>14 day scan) [itmIMPERI] = 'Yes'
 - Porencephalic cysts (>14 day scan) [itmIMPOREN] = 'Yes'
 - Ventriculomegaly (97 percentile plus 4mm) (>14 day scan) [itmIMVENTRI] = 'Yes'
 - Hydrocephalus (>14 day scan) [itmlMHYDRO] = 'Yes'
- Encephaloclastic porencephaly (>14 day scan) [itmlMENCEPH] = 'Yes'

32 33

34

35

36 37

- 'Brain injury' will be set to 'missing' if:
 - the '<14 day scan' is performed >1 day late AND there is no grade 3-4 IVH identified; OR,
 - the '>14 day scan' is performed >1 day early AND none of the criteria applicable to this scan listed above are met; OR,
 - the '>14 day scan' is performed > 7 days after Week 36 AND deemed invalid on blinded clinical review.

38 39 40

'Brain injury' will be set to 'No' if none of the conditions above apply.

- Other types of brain injury recorded as free text in the database will undergo a blinded clinical
- 43 review against the criteria above.

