6.7 Safety Data Analysis

A descriptive analysis of SUSAR data will be conducted by treatment allocation. The event rate is expected to be low, and thus an exact test would be an appropriate choice to perform any formal comparisons between the two groups in the proportion experiencing a SUSAR.

7 Subgroup Analyses

Consistency of the treatment effect on the primary endpoint across subgroups will be tested by including a treatment-by-subgroup interaction term (along with the relevant main effect terms) as covariates in the analysis model (as specified in Section 6.4).

The subgroups of interest are: (i) birthweight <1000 g versus 1000-1499 g; (ii) randomised ≤72 hr versus >72 hr from birth; (iii) those who received versus did not receive probiotics by 36 weeks corrected gestation (note: this is a post-baseline covariate); (iv) ≤ 28 weeks versus >28 weeks gestation at birth. Because 'probiotic use by week 36' is a post-baseline covariate, an unbiased evaluation of its role as an effect-modifier will be attempted by categorising participating sites (NICUs) into tertile subgroups according to their propensity to use probiotics, and evaluating consistency of the treatment effect across these sub-groups.

Adjusted Analyses

8.1 **Stratification Factors**

Sensitivity of results obtained from the primary analysis of the primary endpoint to adjustment for stratification factors will be explored by included them as covariates in the model (See Section 6.4).

4 5 6

7

8

9

10

11

14

15

16

1

2

3

- Randomisation is stratified by gender, birth weight (<1000 g vs ≥1000-1499 g), according to whether the baby is from a single or multiple birth, and site (NICU). Given the modest number of patients at some sites, and the degree of variation in the number of babies recruited across sites (i.e. minimum is less than 10 babies and the maximum is more than 200 babies), sites will be categorised into larger groups that have a comparable pooled primary endpoint event rate. This will be done by estimating, in a blinded fashion, the event risk at each site pooled across treatments, and deriving 'risk classification' according to tertiles. Risk classification will be used as the covariate in the
- 12

13 adjusted analyses in preference to 'individual site'.

8.2 **Treatment Compliance**

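### The early head scan that supplies the IVH grade has no lower time limit relative to randomisation, so a lesion already seen at entry can be scored as a brain-injury and primary event

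*SAP*

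**What the plan says.** - **Entry.** The key eligibility criteria in SAP Section 1 admit babies who are "<1500 g birth weight, ≤7 days old and expected to survive". Entry late in that week is expected, since Section 7 plans a subgroup comparison of babies "randomised ≤72 hr versus >72 hr from birth".
- **IVH item.** In Section 2.3, brain injury is positive if any one of seven items is met. The first is "Worst grade of IVH seen (<14 day scan) [itmIVHGRADE"] at grade 3 or 4.
- **Timing rule for that scan.** Brain injury becomes missing if "the '<14 day scan' is performed >1 day late AND there is no grade 3-4 IVH identified". This is the only timing condition on the early scan. It concerns lateness alone, and it does not apply once a grade 3-4 lesion has been found.
- **Link to the primary endpoint.** Under Section 2.1, babies who "meet at least one of the morbidity criteria will be categorised as having had an event". The same section adds that "The estimated treatment effect will consequently reflect the impact of bLF on the" chance of death or morbidity. Section 5 makes brain injury one of the five key secondary endpoints.
- **Baseline and sensitivity work.** IVH at entry is not named among the baseline variables in Section 6.2. It is also absent from the sensitivity analyses in Sections 6.4 and 6.5, the subgroups in Section 7 and the covariates in Section 8.1.

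**The concern.** An outcome should be something that could still happen after allocation. The window for the early scan has an end but no start, while randomisation may come as late as day 7. A baby scanned on one of the first days, found to have grade 3-4 IVH and then randomised, meets the primary endpoint at entry. Nothing in Section 2.3 sets that baby apart from one whose lesion arose under study treatment.

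Such babies add events that treatment cannot alter, with the same expected frequency in each arm. The estimated relative risk for the composite moves towards 1 and some power is lost. The brain-injury key secondary suffers more, because the same babies form at least as large a share of its smaller number of events. A weak brain-injury result would then be harder to read: it could mean no effect, or it could partly reflect lesions present at entry.

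**Working it through.** **Step 1. Set the time windows side by side.**

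| Element | Source | Window |
|---|---|---|
| Randomisation | Section 1 | Birth to day 7 |
| Early scan supplying the IVH grade | Section 2.3 | No stated start; up to about day 14 |
| Check of scan date against randomisation date | Section 2.3 | None |

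A scan on days 1 to 6 can precede randomisation and still fill the IVH item. Blinded clinical review does not close the gap. Section 2 reserves it for babies for whom the instructions are unclear, and here they are clear. Within Section 2.3 it is directed at free-text injuries and at late second scans.

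**Step 2. Direction and size of the dilution.** The SAP states no sample size, event rate, target effect or IVH rate for LIFT, so there is no figure of its own to reproduce. Every input below is an assumption:

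- f, the share of control-arm primary events that are events only because of a pre-randomisation IVH: 5%, 10%, 15%
- true RR for all other events: 0.80
- control-arm risk: 25%
- babies per arm: 750
- test: two-sided 5%, ignoring sibling correlation

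Observed RR = f + (1 − f) × 0.80:

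- f = 5%: 0.05 + 0.95 × 0.80 = 0.81
- f = 10%: 0.10 + 0.90 × 0.80 = 0.82
- f = 15%: 0.15 + 0.85 × 0.80 = 0.83

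**Step 3. What an exclusion would recover.** Use z = |log RR| / √[(1 − p0)/(n p0) + (1 − p1)/(n p1)], with p1 = p0 × RR, and power = Φ(z − 1.96).

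- *Included:* n = 750, p0 = 0.25, RR as in Step 2.
- *Excluded:* n = 750 × (1 − 0.25f), p0 = 0.25(1 − f)/(1 − 0.25f), RR = 0.80.

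For example, at f = 10%:

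- Included: p1 = 0.205, the standard error is 0.0958 and z = 0.1985/0.0958 = 2.07.
- Excluded: n = 731.25, p0 = 0.2308, p1 = 0.1846, the standard error is 0.1029 and z = 0.2231/0.1029 = 2.17.

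| f | z included | Power included | z excluded | Power excluded | Gain (points) |
|---|---|---|---|---|---|
| 5% | 2.19 | 59.1% | 2.24 | 61.0% | 1.9 |
| 10% | 2.07 | 54.5% | 2.17 | 58.2% | 3.7 |
| 15% | 1.95 | 49.8% | 2.09 | 55.4% | 5.6 |

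The calculation is simplified: it removes only babies whose sole event is the early lesion. Excluding every baby with such a lesion would also remove some who had another event.

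**Step 4. Brain injury alone.** The formula in Step 2 applies with f replaced by the share of brain-injury events already seen at entry. Every baby counted in f is a brain-injury event, and brain-injury events are a subset of primary events among babies with complete data. That share is therefore at least f, and the attenuation at least as large. The SAP gives nothing from which to put a number on it.

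**The case against.** The strongest reply is that the SAP may not be where this is settled. Section 1 lists only key eligibility criteria, and the SAP describes itself as adding detail to a protocol that is not at hand. Exclusions, scan practice and eCRF guidance could each prevent or date an early lesion. Section 2.3 also speaks of a single early scan judged for lateness, which suggests one assessment with a target day. All of this stands as a limit on how often the problem arises. It does not change the derivation rule, which as written lets a scan before randomisation count.

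The plan also has partial checks. The components are analysed separately, and the 72-hour subgroup contrasts babies with more and less opportunity to be scanned before entry. Neither isolates lesions present at entry, but together they mean that a null brain-injury result would not be wholly uninterpretable.

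A reader might infer more than the text supports:

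- *That the primary comparison is biased in favour of one arm or its error rate inflated.* It is not. Under no treatment effect these events create no expected difference.
- *That any scan in the first fortnight feeds the item.* The reference to the worst grade may hint at several scans, but the SAP does not say so.
- *That Section 6.2 rules out reporting IVH at entry.* Its list is introduced as variables that are included, so it need not be complete.
- *That power falls steeply.* A trial sized for 80% power (P = 25%, RR 0.80) would drop to about 77% to 60% if 1% to 5% of all babies were affected. That compares with a trial of the same total risk and no such lesions, and excluding babies cannot recover that difference.

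**Conclusion.** The gap in Section 2.3 is real: the rule can score a lesion seen before allocation as a brain-injury and primary event. The ITT comparison remains valid and type I error is untouched. The harm is attenuation and some loss of interpretability, mainly for the brain-injury component.

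The size is unknown. Under the assumed inputs, a true RR of 0.80 is seen as 0.81 to 0.83, and excluding the babies gains about 2 to 6 percentage points of power. These figures rest on an assumed 5% to 15% share of events, 25% control risk and 750 babies per arm, none of which is in the SAP. If the protocol or eCRF guidance already keeps pre-randomisation lesions out, the effect is nil and a cross-reference would suffice. This is a cheap improvement to the plan, not an error that threatens its main conclusion.

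**What to change.** Keep the composite and the ITT primary analysis as they are, and add three things:

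1. **Section 6.2:** report by arm the number of babies with grade 3-4 IVH on a scan dated before randomisation.
2. **Sections 6.4 and 6.5:** pre-specify one sensitivity analysis of the primary and brain-injury endpoints that excludes those babies, using the same model.
3. **Definition of the exclusion:** any scan dated before randomisation that shows grade 3-4 IVH, whatever later scans show. If the rule used the date of the worst grade instead, a grade 3 lesion at entry that became grade 4 later would carry a post-randomisation date. Membership of the analysis set would then depend on what happened after allocation. Defined as above, the exclusion uses only pre-randomisation information and the comparison stays randomised.

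The cost is a few lines of SAP wording, one baseline row and one extra analysis. The lateness rule in Section 2.3 already needs a scan date, and Section 2.7 already uses the randomisation date. Before finalising, check whether the eCRF holds a date for each early scan or only one for the worst grade; if only one, some lesions cannot be dated reliably. The analysis set is slightly smaller, and the correction is partial because a lesion first scanned after randomisation may have been present before it.

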6.5 Analysis of Categorical Secondary Endpoints

- 26 Secondary categorical endpoints include: survival to hospital discharge (Section 2.2), brain injury
- 27 (Section 2.3), NEC (Section 2.4), LOS (Section 2.5), RoP (Section 2.6), chronic lung disease (Section
- 28 2.9), and survival and development status at 24-36 months corrected gestational age (Section 2.11).

29

- 30 Secondary categorical endpoints will be analysed using the same modelling approach applied to the
- 31 primary endpoint (i.e. a log-binomial model fitted using generalised estimating equations to
- 32 accommodate possible correlation of data between siblings from multiple births. If the log-binomial
- 33 model does not converge, a logistic model will be used).

- 35 Sensitivity analyses will be undertaken on the categorical morbidity endpoints (i.e. brain injury, NEC,
- 36 LOS, RoP, and chronic lung disease) in which any missing values due to death are treated as an
- 37 event. An analysis of survival to 36 weeks may also be undertaken as a sensitivity analysis. Estimates
- 38 of the treatment effect on survival to hospital discharge that are adjusted for adherence will be
- 39 produced using the methods detailed in Section 8.2 in a sensitivity analysis.

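### Section 2.3 has no rule for a scan that was not done, so the brain injury endpoint defaults to 'No'; its 'Yes' and 'missing' rules also overlap without stated precedence

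*SAP*

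**What the plan says.** Section 2.3 derives brain injury from two scans, one before and one after 14 days.

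- **Yes.** The endpoint "will be set to 'Yes' if any of the following conditions are met": grade 3 or 4 IVH on the <14 day scan, or any of six findings on the >14 day scan.
- **Missing, rule 1.** "the '<14 day scan' is performed >1 day late AND there is no grade 3-4 IVH identified".
- **Missing, rule 2.** "the '>14 day scan' is performed >1 day early AND none of the criteria applicable to this scan" is met.
- **Missing, rule 3.** "the '>14 day scan' is performed > 7 days after Week 36 AND deemed invalid on blinded clinical review".
- **No.** The endpoint "will be set to 'No' if none of the conditions above apply".

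Section 2.1 carries the result into the primary endpoint. "Babies that survive to discharge but have missing data for any of the morbidities listed above will be" given a missing primary endpoint, event='No' requires that no morbidity is missing, and a baby who dies before discharge or meets any morbidity criterion is an event.

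Section 6.5 plans sensitivity analyses for brain injury, NEC, "LOS, RoP, and chronic lung disease) in which any missing values due to death are treated as an" event. Section 6.4 offers multiple imputation and best/worst-case scenarios for missing primary endpoint data, as sensitivity analyses only. Section 2 sends cases where the instructions are unclear to blinded clinical review.

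**The concern.** The rules give a more definite answer to a baby with less information. A negative scan two days off time can be set aside as missing, while no scan at all is read as evidence of no injury.

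Brain injury is both a component of the primary composite and one of the five key secondary endpoints adjusted for multiplicity in Section 5. An unscanned survivor without another event enters the primary analysis as a confirmed non-event. Because nothing is flagged as missing, neither the imputation nor the best/worst-case scenarios in Section 6.4 will touch that baby.

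The second problem is that one baby can satisfy both a 'Yes' and a 'missing' condition. Two programmers could code the same baby differently, and Section 2.1 passes the ambiguity on: a survivor with a qualifying finding and a 'missing' flag fits both the missing and the event sentence.

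**Working it through.** Section 2.3 states no figure to reproduce, so the check is of the logic.

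**Inputs.** The rules were applied as written to every combination of scan states.
- <14 day scan, 5 states: absent; on time or more than 1 day late, each with or without grade 3-4 IVH.
- >14 day scan, 9 states: absent; on time, more than 1 day early, more than 7 days after week 36 and judged valid, or the same and judged invalid, each with or without a listed finding.
- Combinations: 5 × 9 = 45.

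**Result as written.** 18 'Yes' only + 9 'missing' only + 6 'No' + 12 both 'Yes' and 'missing' = 45.

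**The six 'No' combinations.** Two have both scans done, negative and acceptable. The other four have an absent scan:
1. neither scan done;
2. only an on-time negative <14 day scan;
3. only an on-time negative >14 day scan;
4. only a negative >14 day scan more than 7 days after week 36 and judged valid.

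**The twelve double classifications.** Rules 1 and 2 exempt a positive finding only on the same scan; rule 3 exempts none.
- In 3 of the 12, the only finding is on a >14 day scan judged invalid. Setting these to missing is defensible.
- In the other 9, a finding stands on a scan not judged invalid. Examples: grade 3-4 IVH on a timely <14 day scan with a negative >14 day scan more than 1 day early (rule 2); periventricular leukomalacia on a timely >14 day scan with a negative <14 day scan more than 1 day late (rule 1).

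These are counts of rule combinations, not of babies.

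**Which analyses the default reaches.**
- *Surviving, unscanned, no other event:* brain injury 'No', so primary event='No'. The primary analysis is affected.
- *Died, no scan:* the primary endpoint is an event by death, so the composite is unaffected. The component is 'No' rather than missing, so the Section 6.5 analysis does not convert it to an event.

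**Illustration for the component, on assumed figures only.** Let p be the component rate and d the share of randomised babies who die with an absent scan and are coded 'No'. Coding them missing moves the main rate from p to p/(1 − d); counting them as events gives p + d. Assume p = 6% and 5% mortality.
- Half of the deaths in this group (d = 0.05 × 0.5 = 2.5%): 6/97.5 = 6.2% and 6 + 2.5 = 8.5%.
- None (d = 0): no change.
- All (d = 5%): 6/95 = 6.3% and 6 + 5 = 11%.

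On these assumptions the main component rate barely moves, and the sensitivity analysis is where the coding shows.

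**Primary endpoint, in symbols.** If a share u of an arm consists of survivors coded event='No' only by this default, coding them missing raises that arm's crude event proportion from q to q/(1 − u). The crude relative risk is multiplied by (1 − u in control)/(1 − u in bLF), which is 1 when the shares are equal.

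**The case against.** **Absent data may be missing by convention.** The NEC and sepsis tables in Sections 2.4 and 2.5 have no row for a blank item either, yet Sections 2.1 and 6.5 speak of missing morbidity data. On this view the Section 2.3 list only adds timing rules for scans that were done. This is a fair guess at intent, and it means the text does not show that unscanned babies were *meant* to be 'No'. But Section 2.3, unlike those tables, has an explicit catch-all. Because its literal result is clear, the Section 2 review of unclear cases would not be triggered.

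**Confirmed injuries are not stated to be lost.** A reader might infer that the missing rules overwrite a confirmed injury. The SAP does not say so. 'Yes' is listed first, the same-scan exemptions suggest that positives were to be kept, and a baby meeting two rules could go to blinded review. This objection stands: loss of a finding is one possible reading (rules run in sequence, last one wins), not the stated rule. The missing precedence still needs repair.

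**Deaths cannot distort the composite.** This also stands. Only the component and its sensitivity analysis are affected by babies who die unscanned.

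**Not every off-time scan is missing.** Correct. A late >14 day scan is missing only if it is more than 7 days after week 36 and blinded review judges it invalid, and rules 1 and 2 protect a positive finding on the off-time scan itself.

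**Conclusion.** The point holds in two parts. First, Section 2.3 has no rule for a scan not performed. Read literally, its default codes such a baby 'No' when there is no qualifying finding and no missing rule applies to the other scan. That puts unscanned survivors with no other event into the primary analysis as morbidity-free, defeats the safeguard in Section 2.1, and leaves the Section 6.5 death-as-event analysis without the babies it was written for. Second, 'Yes' and 'missing' overlap in 12 of 45 rule combinations, 9 of them with a finding on a scan not judged invalid, and no precedence is stated in Section 2.3 or 2.1.

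The size of the effect cannot be computed, because the SAP gives no frequency of absent or off-time scans. The percentages in the illustration are assumptions and say nothing about this trial. The document does not support a claim that confirmed injuries are overwritten, that deaths bias the composite, or that the relative risk is biased in a known direction.

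**What to change.** Replace the Section 2.3 rules with an ordered set:

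1. 'Yes' if any listed criterion is met on a scan not deemed invalid on blinded review, whatever the status of the other scan.
2. Otherwise 'missing' if either required scan was not done, fails its timing rule, or is deemed invalid. If some babies are not scanned by policy, name that group and state its code explicitly.
3. Otherwise 'No'.

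Add to Section 2.1 that an event takes precedence over a missing morbidity. The validity condition in step 1 matters: without it, a finding seen only on a scan that blinded review rejected under rule 3 would count.

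Applied to the same 45 combinations, the ordered rules give 18 + 9 = 27 'Yes', 9 + 3 + 4 = 16 'missing' and 6 − 4 = 2 'No', with no overlap.

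The work is SAP wording and derivation code, to be settled before unblinding. The real cost is that some more survivors will have a missing primary endpoint and drop out of the primary analysis; multiple imputation addresses them only in the Section 6.4 sensitivity analysis. A table of absent, off-time and invalid scans by arm would show how much this matters.
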